7.3.5 Sexual Partners – IDI Visit

Up to 30 sexual partners will be screened and enrolled to take part in a single IDI within 1 month of their participant partner's completion of product use (Visit 9 or SEV). Members of the protocol team and site teams will collaboratively determine which sexual partners to contact from among those that participants have given written permission during screening and enrollment for the study team to contact. Permission to contact sexual partners will be confirmed at Visit 9/SEV, and – if confirmed – sites will contact sexual partners according to site SOP and/or local IRB/IEC guidelines. Participants may change their decision about their sexual partners' involvement at any time during the study. Selection of sexual partners to invite for an IDI will be purposive so that characteristics/experiences of the enrolled study participant, order of IVR use, study site, and a breadth of perspectives and experiences are represented. Selection criteria and procedures are further described in the MATRIX-003 SSP Manual. See Section 7.6.2 for further details about the IDI subset.

Table 6: IDI Visit with Sexual Partner Subset

IDI Visit with Sexual Partner Subset – Screening and Enrollment Procedures	
Component	Procedures
Administrative and Regulatory	
 Confirm eligibility Obtain written informed consent Assign a unique PTID Number Collect demographic data Collect locator information Provide reimbursement for study visit
Behavioral	
 Administer brief behavioral questionnaire (including social harms/benefits assessment) Conduct sexual partner IDI – within 1 month of participant Visit 9

Multiple visits may be conducted to complete all required procedures, if necessary.

7.4 Follow-up Procedures for Participants Who Permanently Discontinue Study Product

7.4.1 Participants Who Become Infected with HIV

If a participant tests positive for HIV after the Enrollment Visit, the participant will be referred to local care and treatment services and (at sites with capacity to offer as standard of care and per site SOP) may return to the research clinic for additional testing, counseling, and other support services as needed. Continued study participation would be of no added benefit to the participant, thus follow-up visits and procedures will be discontinued, study product use will cease, and the participant will be considered terminated from the study. An Early Termination Visit will be conducted, if the participant is willing (see Section 7.3.4). Please reference the MATRIX-003 SSP Manual for additional details.

7.4.2 Participants Who Become Pregnant

If a participant becomes pregnant after the Enrollment Visit, the participant will be referred to local health care services and (at sites with capacity to offer as standard of care and per site SOP) may return to the research clinic for additional counseling services as needed. Continued study participation would be of no added benefit to the participant, thus study product use will cease, follow-up visits and procedures will be discontinued, and the participant will be considered terminated from the study. An Early Termination Visit will be conducted, if the participant is willing (see Section 7.3.4). Please reference the MATRIX-003 SSP Manual for additional details.

7.4.3 Participants Who Permanently Discontinue Study Product Use for Other Clinician-Initiated Reasons

Participants who permanently discontinue study product use for any clinician-initiated reason other than HIV infection or pregnancy may, after consultation with the PSRT and MATRIX-003 Management Team, have their remaining study follow-up visits and procedures discontinued. Participants will, however, be asked to complete an Early Termination Visit, if willing (see Section 7.3.4). In the event study follow-up is continued, participants will have the protocol-specified visits until completion of the current study stage. Sites should contact the PSRT and management team to determine whether the participant should be followed on study and what study procedures should be completed.

Participants who permanently discontinue study product use due to an adverse event (AE) must continue to be followed up in the study, if willing, until resolution (return to baseline) or stabilization of the AE is documented.

7.5 Interim Visits/Contacts

Interim visits/contacts (i.e., between regularly scheduled visits) may be performed as needed (e.g., participant reports an AE) at any time during the study, and any visit/contact procedures may be conducted as indicated. All interim contacts and visits will be documented in participants' study records. If a participant misses a visit, the participant can come to the clinic for an interim visit to make up certain missed visit procedures and specimen collections, and the instance(s) will

be documented as a protocol deviation. Refer to the MATRIX-003 SSP Manual for additional details.

7.6 Behavioral Evaluations

The study will address questions related to the primary and exploratory objectives of acceptability, exploratory objective of social harms and social benefits, and both participants' and sexual partners' attitudes towards and experiences with the IVR. The study will assess ring use facilitators and challenges experienced by participants, from the perspectives of both participants and a subset of sexual partners. The study will also explore participants' and sexual partners' views on acceptable approaches to support study product adherence. These questions will be assessed via behavioral questionnaires and IDIs conducted by trained interviewers/facilitators. In addition, the study aims to gain further insight on:

- Product insertion and removal
- Attitudes towards and experiences with using the IVR
- Previous IVR use experience
- Perspectives on any changes in vaginal environment
- Comparisons between the two IVRs and comparisons to existing HIV prevention options
- Factors related to future willingness to use/recommend the IVR
- Sexual partner attitudes towards and experiences with the IVR, and their perspective of participant's attitudes and experiences

Additional questions and probes will be designed to delve further into the social and cultural norms that may play a role more broadly in product use.

Table 7 outlines a summary of the assessment methods that will be used and the specific components of acceptability that will be assessed, informed by previous work and the Theoretical Framework of Acceptability (TFA) as presented in Ortblad et. al. [9]

Table 7: Summary of behavioral assessments and alignment with TFA

Assessments and Timepoints	Acceptability components measured
Baseline questionnaire (Visit 2)	Affective attitude, burden, opportunity costs, barriers/benefits
Telephone-based brief questionnaires (Visits 3 and 7)	N/A
Mid-point questionnaires (Visits 4 and 8)	N/A
Follow-up questionnaires (Visits 5 and 9)	Affective attitude, burden, opportunity costs, overall satisfaction, usability, appropriateness, preferences, perceived barriers/benefits
Social harms assessments (All clinic visits after Screening)	N/A
Social benefits assessments (Visits 5 and 9)	N/A

Assessments and Timepoints	Acceptability components measured
Participant IDI (Ideally at or within 1 week of Visit 9/SEV but no later than 3 weeks after SEV)	Affective attitude, burden, satisfaction, usability, appropriateness, perceived barriers/benefits
Sexual partner IDI (Within 1 month of Visit 9/SEV)	Affective attitude, burden, satisfaction, usability, appropriateness, perceived barriers/benefits

7.6.1 Quantitative Behavioral Assessments

Behavioral questionnaires at enrollment and during follow-up will measure key dimensions of acceptability pertinent to the IVR in its current phase of development alongside women's experiences in using the ring during the study. In addition, behavioral questionnaires will measure vaginal practices, contraceptive use, HIV prevention behaviors, sexual behavior and relationship factors, social harms, and social benefits. These questionnaires will be used to assess factors correlated with placebo IVR acceptability and use experiences. Additionally, quantitative questionnaire data will be complemented by data captured through structured SMS/phone visits, and through IDIs with subsets of participants and sexual partners.

7.6.2 Qualitative Behavioral Assessments

Two sets of IDIs will be completed. The first will be conducted with a subset (up to 30, approximately 6 per site) of participant ring users who will be purposively selected and invited to complete an IDI after their scheduled removal of the second ring. The IDI will ideally take place at or within 1 week of Visit 9/SEV but no later than 3 weeks after Visit 9/SEV. Selection of participant ring users to invite for an IDI will be purposive so that order of IVR use, study site, and a breadth of perspectives and experiences are represented. Selection criteria and procedures are further described in the MATRIX-003 SSP Manual. Additionally, a subset of sexual partners of participants (up to 30, approximately 6 per site) will be purposively selected to participate in an IDI, which will take place within approximately 1 month of receipt of confirmation of permission to contact the sexual partner at Visit 9/SEV. We will explore participant experiences using the IVR, acceptability of different attributes of the ring, and social factors influential to attitudes toward the IVR as a future HIV and/or dual purpose (HIV and pregnancy) prevention option. We will also explore sexual partner views on the IVR and their perceptions of and experience with the IVR during sexual activity. IDIs will be conducted separately with participants and sexual partners to assess these topics. IDIs will include, but not be limited to, the following topics:

- Descriptions of ring insertion practices
- Main challenge(s) encountered with ring use, especially during sex
- Potential changes to the ring
- Other factors (e.g., situational, relationship, trial-specific, social/cultural/economic, sex and menstruation related, vaginal practices, previous IVR use) influencing ring acceptability and use experience
- Sexual partner attitudes towards and experiences with the IVR, and their perspective of participant's attitudes and experiences
- Perspectives and attitudes regarding monthly IVR use for HIV prevention and/or as a dual purpose IVR for HIV and pregnancy prevention

The IDIs with sexual partners will also include the following discussion topics:

- Knowledge/understanding of MATRIX 003 and the study product
- Experiences of sex with clinical study participant during the time they were using study product

Semi-structured IDI guides will be developed by qualified social scientists and administered by trained interviewers. Guides will contain key research questions relating to the main topics of interest and suggested probes. Interviews and discussion sessions will be audio-recorded and transcribed.

7.7 Protocol and Product Adherence Counseling

Counseling will be provided by different site staff than those conducting the behavioral questionnaires when feasible, in accordance with standard study methods and as specified in site SOPs. Contraception counseling will be provided to participants of childbearing potential at Screening and, if indicated, at subsequent clinic visits. Protocol adherence counseling will be provided at all clinic visits beginning at the Screening Visit. Participants will receive study product counseling upon enrollment into the study and at subsequent follow-up visits as appropriate to the visit. Study staff will document administration of study product (at Visits 2 and 6) and that the counseling was provided. Counseling also will include reminders regarding concomitant medication, sexual activity, intravaginal product use and practices, and behavioral restrictions during study participation (as specified in Section 6.7).

7.8 Clinical Evaluations and Procedures

Physical Examination and Medical History

The full physical examination will include the following assessments:

- Vital signs
 - Blood pressure
- Measurements of weight and height
- General appearance
- Cardiac exam
- Respiratory exam
- Abdomen

Participants will be asked about medications/therapies at every visit, including Screening. Study staff will ask about adverse events at all visits beginning at Enrollment. A full physical examination will be completed by a clinician at Screening. Thereafter, a directed physical examination will be performed to assess any complaints or symptoms with which the participant presents at the follow-up visits as clinically indicated.

Pelvic Examination (at all regularly scheduled clinic visits and as needed for AE assessment)

- Pelvic exams will be performed using visual inspection of external genitalia.
- Speculum examination for visualization of the cervix and vagina.
- Bimanual exam may be performed as needed (required at Screening Visit).
- Digital exam to assess ring placement (required at Insertion Visits).
- Cervicovaginal fluid (CVF) will be collected using swabs to characterize the microbiome and assess for STI as indicated in Appendix I.

Additional clinical assessments/procedures may be performed at the discretion of the examining clinician in response to symptoms or illnesses present at the time of the exam/procedure.

7.9 Laboratory Evaluations

Local Laboratory

- Saliva (only at sites with CLIA certification)
 - HIV test(s)
- Urine
 - Urine pregnancy test
 - Urine dipstick/culture (as indicated and/or per local standard of care)
- Blood
 - HIV test(s) (not required for sites that conduct saliva testing)
 - CBC
 - Serum creatinine
 - AST/ALT
 - Syphilis serology
- Pelvic
 - NAAT for GC/CT/TV (at sites with capacity)
 - Pap test (if indicated [if participant is unable to provide documentation of a normal Pap test within 3 years prior to enrollment])
 - Vaginal pH
 - KOH wet mount for candidiasis and/or BV (if indicated)

Designated Laboratory

- Blood
 - Plasma for archive
- CVF
 - NAAT for GC/CT/TV (at sites without capacity)
 - Gram stain for Nugent score
 - Microbiota (Quantitative PCR)
 - Vaginal swab(s) for archive

Only Local Laboratory test results will be provided to the participant. Once all required study analyses of collected specimens are complete, any remaining samples may be shipped to OCIS for use in study-related quality assurance and quality control testing. If study samples will be used for assay validation or proficiency testing that is not study related, all participant identifiers (PTID) will be removed from the samples prior to use. Specimens obtained from participants who do not consent to long term storage will not be used for assay validation or proficiency testing purposes.

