5.3 Exclusion Criteria

Potential participants must not meet any of the following criteria prior to Enrollment (unless otherwise specified):

- 1) Per participant report at Screening and Enrollment, intends to do any of the following during the study participation period:

- Become pregnant.
- Breastfeed.
- Relocate away from the study site.
- Travel away from the study site for a time period that would interfere with product resupply and/or study participation.

- 2) Positive HIV test at Screening or Enrollment.
- 3) Positive test for *Trichomonas vaginalis* (TV), *Neisseria gonorrhoea* (GC), *Chlamydia trachomatis* (CT), or *Treponema pallidum* (Syphilis) at Screening and (per participant report) treated for potential STI within past 12 months.
- 4) Diagnosed with urinary tract infection (UTI), pelvic inflammatory disease (PID), or reproductive tract infection (RTI) requiring treatment per WHO guidelines at Enrollment.

Note: Otherwise eligible participants diagnosed during screening with a UTI, symptomatic yeast infection or symptomatic BV infection are offered treatment consistent with WHO recommendations. If treatment is completed and symptoms have resolved within 45 days of obtaining informed consent for screening, the participant may be enrolled.

- 5) Clinically apparent Grade 2 or higher pelvic exam finding per the DAIDS Table for Grading Adult and Pediatric Adverse Events, Corrected Version 2.1, July 2017 and/or Addenda 1 (Female Genital Grading Table for Use in Microbicide Studies [Dated November 2007]) at Enrollment.

Note: Otherwise eligible participants with exclusionary pelvic exam findings at Screening may be enrolled/randomized if treatment is completed at least 7 days prior to enrollment and findings have improved to a non-exclusionary severity grading or resolved by the time of enrollment. Spotting/bleeding will be considered exclusionary only if greater than what would be expected from contraceptive use.

- 6) Participant report and/or clinical evidence of any of the following:
 - Known adverse reaction to silicone (ever).
 - Use of diaphragm, NuvaRing, or spermicide for contraception starting 2 weeks prior to Screening through Enrollment.
 - Use of any of the following in the past 12 months: stimulants (cocaine [including crack], methamphetamine, or non-physician prescribed pharmaceutical-grade stimulants), or inhaled nitrates, or illicit injection drug use of any kind.

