7.2 Screening Visit

Potential participants will provide written informed consent prior to any study procedures, including all screening assessments to determine their eligibility to take part in the study. Participants will be counselled to abstain from penetrative vaginal sex for the first 14 days after each insertion of study product, and from use of intravaginal products and practices (see Section 6.7) for the full duration of study participation. Eligibility determination will include baseline demographics and medical history, physical and pelvic examination, urine pregnancy test (UPT), and HIV and STI screening. If a potential participant is not eligible, screening will be discontinued once ineligibility is determined. If a potential participant has symptoms of an STI, RTI or UTI, they will be referred to local care and treatment services or (at sites with capacity and per site SOP) be given treatment according to the local standard of care.

If eligible, potential participants will return within 45 days for their Enrollment Visit. For women with a regular menstrual cycle, the Enrollment Visit (and Visit 6 if enrolled) will ideally be scheduled when the potential participant is not menstruating.

Note: Multiple visits may be conducted to complete all required screening procedures, including any procedures that need to be repeated (e.g., blood draw), if necessary.

Note: Potential participants who fail their first screening attempt may be re-screened once.

Table 1: Screening Visit

Screening Visit – Visit 1		
Component	Procedures	
Administrative and Regulatory	
 • Obtain written informed consent for screening and enrollment (sites may split screening and enrollment consent if requested/required by IRB/IEC) • Assign a unique Participant Identification (PTID) number • Assess eligibility • Collect demographic information • Collect locator information • Provide reimbursement • Schedule next visit/contact* 	
Behavioral/Counseling	
 • HIV pre- and post-test counseling • HIV and STI risk reduction counseling • Protocol counseling (including contraception and restrictions around vaginal activity) 	
Clinical	
 • Collect medical and menstrual history • Collect concomitant medications • Perform full physical examination • Perform pelvic examination (including bimanual exam) • Provide available test results • Treat or prescribe treatment for RTI/UTI/STIs* 	

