Laboratory	Saliva	
 • HIV test(s) (only at sites with CLIA certification)
	Urine	
 • Urine pregnancy test • Urine dipstick/culture*
	Blood	
 • HIV test(s) (not required for sites that conduct saliva testing) • Complete blood count (CBC) • Serum creatinine • AST/ALT • Syphilis serology
	Pelvic	
 • Nucleic acid amplification test (NAAT) for GC/CT/TV • Pap test^ • Saline/potassium hydroxide (KOH) wet mount for candidiasis and/or bacterial vaginosis (BV)*

*If indicated and/or per local standard of care; ^ if indicated (if participant is unable to provide documentation of a normal Pap test within 3 years prior to enrollment)

7.3 Follow-up Visits/Contacts – Stages 1 and 2

Within 45 days of the Screening Visit, willing and eligible participants will have their eligibility confirmed and be randomized (1:1) to IVR sequence at Enrollment (Visit 2). If not enrolled within 45 days, participants will need to be rescreened. Stage 1 (1st assigned IVR) and Stage 2 (2nd assigned IVR) are almost identical with a period of no fewer than 7 days and no more than 21 days of no product use between stages. Participants will be retested for pregnancy and HIV at the beginning of Stage 2 (Visit 6). Any participants testing positive for either will be withdrawn from the study.

7.3.1 Insertion Visits – Visit 2 (Enrollment/Stage 1 Day 0) and Visit 6 (Stage 2 Day 0)

Participants will be counselled to abstain from penetrative vaginal sex for the first 14 days of product use, and from use of intravaginal products and practices (see Section 6.7) for the full duration of study product use. Study staff will review instructional materials about the IVR with participants prior to insertion of the ring. Participants will be asked to provide a urine sample for a UPT, undergo HIV and STI screening and a pelvic examination, and at Visit 2 complete an interviewer-administered baseline acceptability questionnaire about the IVR. Participants will be given instructions regarding ring insertion and then asked to self-insert the ring at the study clinic. After insertion, ring placement will be checked by a clinical team member. If the participant is unable to self-insert the ring correctly after 2 attempts, a clinical team member will assist the participant. Participant attempts to insert the ring will be documented on the appropriate CRF.

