7.3.2 Telephone Contacts – Visits 3 and 7 (Day 7)

Approximately 7 days after the insertion of each IVR, a member of the study team will contact the study participant via telephone or short message service (SMS) to assess participant wellness, comfort with the ring, and any concerns. Participants who report AEs or express concerns may be asked to come in for an Interim Visit, if willing, to conduct additional counseling and/or testing as needed. Participants who prefer to complete these procedures in-person may elect to do so.

Table 3: Telephone Contacts – Visits 3 and 7 (Day 7)

Telephone Contacts – Visits 3 and 7 (Day 7)	
Component	Procedures
Administrative and Regulatory	
 Review/update locator information Provide reimbursement Schedule next visit/contact
Behavioral/Counseling	
 HIV and STI risk reduction counseling* Protocol counseling* Telephone-based brief questionnaire

Telephone Contacts – Visits 3 and 7 (Day 7)	
Component	Procedures
Clinical	
 Review/update medical and menstrual history Review/update concomitant medications AE assessment Provide available test results

*If indicated

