9.5 Other Clinical Findings

A thorough evaluation of genital complaints is expected in the context of this study; however, syndromic management of genital symptoms is acceptable while awaiting laboratory results if such practice is in line with the local standards of care. Observed single dose treatment should be provided whenever possible, per clinician discretion. When clinically appropriate, investigators should use oral or parenteral medications when at all possible.

Product use need not be held in the event of an STI/RTI requiring treatment, unless other permanent discontinuation guidelines apply. Should the IoR/designee determine that a permanent discontinuation is warranted due to an STI or RTI, consultation with the PSRT is required. The IoR/designee should manage STI/RTI per local guidelines or current WHO guidelines, available at <http://www.who.int/en/>. Test for cure is not required after treatment of asymptomatic STIs.

If a suspected finding is reported by the participant between scheduled visits, an interim visit may be scheduled at the discretion of the site investigator.

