15 APPENDICES

APPENDIX I: SCHEDULE OF STUDY VISITS AND EVALUATIONS

STUDY PROCEDURES										
	SCR	Stage 1					7- to 21-day period of no IVR use	Stage 2		
		V1	V2	V3	V4	V5		V6	V7	V8
Day	-45	0	7	14	28		0	7	14	28
Clinic Visit	X	X		X	X		X		X	X
Phone Contact			X					X		
ADMINISTRATIVE AND REGULATORY										
Obtain/review informed consent for screening and enrollment (sites may split screening and enrollment consent if requested/ required by IRB/IEC)	X	*								
Assign a unique PTID	X									
Collect/update/review contact/locator information	X	X	X	X	X		X	X	X	X
Collect demographic information	X									
Assess/confirm eligibility	X	X								
Randomization		X								
Confirm permission to contact sexual partner for IDI (subset)										X
Provide reimbursement	X	X	X	X	X		X	X	X	X
Schedule next visit/contact	*	*	X	X	X		X	X	X	
COUNSELING										
HIV pre- and post-test counseling	X	X		*	*		X		*	X
HIV and STI risk reduction counseling	X	X	*	*	*		X	*	*	X
Protocol counseling	X	X	X	X	X		X	X	X	
Abstinence										
BEHAVIORAL										
Review instructional materials		X					X			
Baseline behavioral questionnaire		X								
Post-insertion behavioral questionnaire		X					X			
Telephone-based brief questionnaire			X					X		
Mid-point behavioral questionnaire				X					X	
Follow-up behavioral questionnaire					X					X
Social harms assessment		X		X	X		X	X	X	
Social benefits assessment					X					X
Participant IDI (subset) (ideally at or within 1 week of V9/SEV but no later than 3 weeks after V9/SEV)										X
Sexual partner IDI (subset) (within 1 month of V9/SEV)										X
CLINICAL										
Collect/update/review medical and menstrual history	X	X	X	X	X		X	X	X	X
Collect/update/review concomitant medications	X	X	X	X	X		X	X	X	X
Physical exam (symptom-directed after Screening)	X	*		*	*		*		*	*
Pelvic exam with speculum (bimanual exam at Screening)	X	X		X	X		X		X	X
Digital exam by clinical team member to confirm IVR placement		X					X			

[figure not shown]
STUDY PROCEDURES		SCR	Stage 1					Stage 2			
			V1	V2	V3	V4	V5				
Day			-45	0	7	14	28	V6	V7	V8	V9
Clinic Visit	X	X			X	X		X		X	X
Phone Contact			X					X			
Clinician assessment of ring insertion or removal experience (# attempts, comfort)			X				X				X
Provide available test results	X	X	X	X	X			X	X	X	X
AE assessment		X	X	X	X	X		X	X	X	X
Treat or prescribe treatment for RTI/UTI/STI	*	*		*	*			*		*	*
LABORATORY											
Saliva	HIV test(s) (only at sites with CLIA certification)		X	X			*	*			X

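### Section 7.9, read literally, keeps a GC/CT/TV NAAT result from the participant at any site that sends the test to the Designated Laboratory

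*Combined protocol and SAP*

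**What the plan says.** Section 7.9 divides testing between a Local and a Designated Laboratory. The GC/CT/TV NAAT appears in both lists: under Local for sites with capacity, and under Designated as "NAAT for GC/CT/TV (at sites without capacity"). The section then sets the rule on returning results: "Only Local Laboratory test results will be provided to the participant". No exception follows.

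Other sections bear on the same result:

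- Table 1 (Section 7.2) lists "Nucleic acid amplification test (NAAT) for GC/CT/TV" as a required Screening test. After Screening, Appendix I stars it as done if indicated or per local standard of care.
- Table 1 also lists "Treat or prescribe treatment for RTI/UTI/STIs", if indicated or per local standard of care. The Section 7.2 narrative provides referral or treatment for potential participants who have symptoms.
- Section 9.5 says that "The IoR/designee should manage STI/RTI per local guidelines or current WHO guidelines", and waives a test of cure after asymptomatic STIs have been treated.
- Section 13.4.1 names distress on learning of an STI as a risk of taking part. Section 13.4.2 offers STI testing, free STI treatment and, for some participants, early diagnosis from study tests.

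**The concern.** The rule on returning results is tied to the laboratory that runs the test, not to the kind of test. For research assays and archive samples that is sensible. For a diagnostic STI test it means that whether a participant is told of gonorrhoea, chlamydia or trichomonas depends on where her swab was sent.

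The person at risk is one with a positive result and no symptoms. Nothing prompts her to seek care, and vaginal sex is unrestricted in the second half of each use period (Section 6.7). Site staff would hold a result that Section 9.5 tells them to manage and that Section 7.9 tells them not to give her.

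**Working it through.** No arithmetic decides this point. The check is a comparison of the text.

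**1. Which results the rule catches.** The Designated Laboratory list has five items: archived plasma, the NAAT at sites without capacity, Gram stain for Nugent score, microbiota PCR, and archived swabs. Of these, only the NAAT feeds an eligibility criterion. Exclusion 3 names four infections, and the NAAT covers three of them. The fourth, syphilis, is tested only locally, so its result can be returned.

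**2. When such a result exists.** Table 1 and Appendix I require the NAAT at Screening. Tables 4 and 5 and Appendix I star it afterwards. The exposure is therefore one required test per person screened, plus any later test done on indication. Sections 7.3.1 and 7.3.4 speak more broadly of STI screening at insertion visits and at Visit 9. I follow the tables, which give the narrower exposure.

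**3. Whether exclusion makes the question moot.** Exclusion 3 needs a positive test together with reported treatment for a potential STI in the past 12 months. A woman with a positive NAAT and no such history is not excluded by it. Exclusion 4 may reach some of these women, through "reproductive tract infection (RTI) requiring treatment per WHO guidelines at Enrollment". Either way, both criteria decide who may enrol; neither decides whether she is told.

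**4. What the other sections need.**

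- Section 9.5 foresees treatment of asymptomatic STIs. Such infections are normally found by testing, and treating one properly means telling the person.
- Section 13.4.1 expects participants to find out that they have an STI.
- Section 13.4.2 promises STI testing and free treatment, with no exception by site or laboratory.

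**5. Whether any other text closes the gap.**

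- The referral provision in Section 7.2 depends on symptoms, so it misses the asymptomatic case.
- Syndromic management under Section 9.5 also depends on symptoms.
- "Provide available test results" stands in Tables 1 to 5 with no limit by laboratory, but it is a general line that Section 7.9 could be read to narrow. It neither cures the conflict nor proves it.
- I found no provision exempting the Designated Laboratory NAAT.

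**6. Size.** There are five sites, and the protocol does not say how many lack NAAT capacity. The range is 0 to 5. It gives no infection rate, so no count of affected participants can be derived.

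**The case against.** The strongest reply is that Section 7.9 is the specific rule and the result-return line in the visit tables is a generic one, covering HIV, pregnancy, blood counts, chemistry, Pap, syphilis and wet mount. A specific rule that narrows a generic line is not a contradiction. That stands, and for this reason the visit-table line is not used here as proof.

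A reader might go further and infer from Appendix I that the sentence clashes with result return at all nine visits and, through "Treat or prescribe treatment for RTI/UTI/STI", with treatment at all seven clinic visits. The documents do not support that. Those rows count occasions when some result may be given or some treatment offered, not occasions when a Designated Laboratory NAAT result exists. A reader might also infer that infected participants would go untreated, or that eligibility could not be judged. Section 7.9 limits only what the participant is given; it bars neither treatment, nor referral, nor the site's own use of the result.

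It can also be said that the statements in Section 13.4 could be met by local syphilis testing, by local NAAT, or by diagnosis from symptoms, and that the only result participants are expressly required to receive is HIV (Section 13.10.1), which is tested locally. This weakens Section 13.4 as evidence but does not dispose of it, because its offer carries no site exception. Nor does it answer the asymptomatic treatment foreseen in Section 9.5, although that sentence names no organism or laboratory.

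Finally, sites would probably return the result anyway, and the SSP Manual or consent forms, which I have not examined, may say so. That is likely. It would still mean departing from an explicit protocol sentence.

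**Conclusion.** Wrong as written; minor, and a matter of participant safety. Taken literally, Section 7.9 withholds the required Screening GC/CT/TV NAAT result, and any later indicated one, from participants at sites without local capacity. This conflicts with Section 9.5 and with Sections 13.4.1 and 13.4.2, and nothing in the protocol body reconciles them. The likeliest explanation is a drafting slip: a sentence meant for the Nugent, microbiota and archive samples that also caught the NAAT.

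Confidence is high on the wording and low on any practical consequence. If every site can run the NAAT, no participant is affected. The conclusion rests on the protocol body alone. The A-versus-B comparison, the sample size and the power are untouched.

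**What to change.** Replace the sentence in Section 7.9 with: *Only Local Laboratory test results, and GC/CT/TV NAAT results from the Designated Laboratory, will be provided to the participant.* Put matching wording in the SSP Manual.

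The cost is one sentence in the protocol and its counterpart in the manual. No test, visit or staff time is added, and the research assays and archive samples stay outside result return.
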